Secondary Endpoint(s)	
 
Change from baseline in the blood (serum) and esophageal TGF-<math>\beta</math> levels in participants receiving losartan potassium at the EOT visit (or at early withdrawal) as determined by research blood samples and EGD with biopsy, respectively.
 
Normalization of the EoE transcriptome in participants receiving losartan at the EOT visit (or at early withdrawal) as determined by EGD with biopsy.
 
Change from baseline in histopathology in participants receiving losartan potassium at the EOT visit (or at early withdrawal) as determined by EGD with biopsy.
 
Change from baseline esophageal compliance in participants receiving losartan at the EOT visit (or at early withdrawal) as determined by EndoFLIP.
 
Change from baseline PFC (Pediatric Eosinophilic Esophagitis Symptom Severity [PEESS], PedsQL Eosinophilic Esophagitis Module [PedsQL™ EoE], EoE Quality of Life Questionnaire, and EEsA) in participants receiving losartan at the EOT visit (or at early withdrawal) as determined by EndoFLIP.
 

Accrual Objective	
 
It is estimated that 30 patients will need to be screened for a total of approximately 15 participants enrolled in the study. Of the 15 participants enrolled, at least one third will have evidence of EoE with CTD, whereas the remaining participants will have no evidence of a CTD.
 

Study Duration	
 
Total duration of treatment is approximately 16 weeks. During the titration phase, participants will be on titrated doses of losartan for 4 weeks. During the maintenance phase, participants will be on a stable dose of treatment for 12 weeks.
 

Treatment Description	
 
• During the study oral administration of losartan tablets or suspension occurs once a day, at about the same time each day, throughout the treatment period. The dose of the study agent to be administered will depend on the participant's body weight and will be calculated (mg/kg) on the basis of a titration schedule during the treatment (i.e., titration and maintenance) phase, not to exceed the daily dose of 100 mg. The medication dosage for losartan potassium will change throughout this study, titrating to a higher dose.
 

------------------------------	---

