### 12.5 Sample Size Considerations

Five patients with EoE-CTD and 10 patients with EoE will be recruited into the study. Since this represents a pilot study to evaluate whether the treatment affects endpoints, the sample size was not selected on the basis of power considerations for statistical testing. The estimates of treatment effect from this study will be used to power future studies. Based on historical data from the [REDACTED], it is estimated that the standard deviation of the change from baseline at 12 weeks based on the square root transformation of the eosinophil/HPF values will be approximately 5. Table 7 provides the width of the two-sided 95% confidence interval for the change from baseline in eosinophil/HPF for various scenarios of sample size and standard deviation.

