This is a phase II, open-label trial of losartan in patients diagnosed with EoE with or without a CTD. Prior to entry, patients must meet the current consensus criteria for EoE in which efforts are made to rule out other causes of esophageal eosinophilia. The trial will perform a preliminary assessment of the effect of the maximum tolerated dose of losartan in participants with active EoE as determined by the absence of side effects and by vital signs being within normal limits. The primary endpoint of the study is the reduction in the number of esophageal eosinophils in participants who will receive losartan orally once a day (Figure 1). The primary safety endpoint is descriptive and will require reporting of SAE or Grade 3 and above AEs.

Figure 1 Study Design Flowchart

Analysis Populations

The analysis population for the primary and secondary endpoints will be participants who received Losartan and maintained the baseline EoE treatment throughout the course of the study.

Statistical Considerations and Analytical Plan

Overview

Change from baseline for eosinophil counts will be calculated for each participant. The average change from baseline within each group and combining both groups (i.e. EoE and EoE-CTD) will be calculated along with the corresponding two-sided, 95% confidence interval. Additionally, we will perform paired tests which will specifically test whether there was significant change between baseline and study completion. The last observation carried forward (LOCF) method will be used for participants who end the trial early. To assess changes over time for continuous secondary and safety outcomes, a mixed effects model for repeated measures analysis will be used. Unless stated otherwise, all statistical testing will be done at $\alpha=0.05$.

Variables of Interest

Primary outcome:

- 1) Change in eosinophils/hpf from baseline to post treatment
- 2) Rate of SAE / Grade 3 or above AE

Secondary outcomes:

- 1) Blood (serum) and esophageal TGF- β levels
- 2) EoE transcriptome
- 3) Histopathology as assessed by the Histology Scoring System (HSS): Will include the overall score, grade score, stage score, and the inflammatory and structural sub-scores. Scores will be reported as distal, proximal, and maximum
- 4) Esophageal compliance as measured by EndoFLIP.
- 5) PROS (Pediatric Eosinophilic Esophagitis Symptom Severity [PEESS], PedsQL Eosinophilic Esophagitis Module [PedsQLTM EoE], EoE Quality of Life Questionnaire, and EEsAI)

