Prior to any hypothesis testing, all variables will be reviewed for plausibility. Any values which are considered suspect will be reviewed by the clinical team to ensure accuracy. Continuous data will be evaluated for distributional assumptions of normality. Natural log-transformation will be considered for right skewed non-normally distributed data (the most typical skew seen in physiologic data).

Demographics/Patients Characteristics

Demographic, patient characteristics, medication use, and study completion status will be summarized using median [interquartile range] for continuous variables and frequency and percentages for categorical variables. Treatment comparisons will be performed for demographics and patient characteristics using the Wilcoxon Rank sum test for continuous variables and the Fisher's Exact test for categorical variables. All tests will be conducted at $\alpha=0.05$.

Analysis of Primary Outcome

Primary Objective:

1. To assess the effect of losartan on the reduction of esophageal eosinophils in participants with EoE with or without a CTD.

Change from baseline for eosinophil counts will be calculated for each participant. The average change from baseline within each group and combining both groups (i.e. EoE and EoE-CTD) will be calculated

along with the corresponding two-sided, 95% confidence intervals. If the assumption of normality is not viable for the change from baseline score, we will use a square root transformation on the eosinophil counts prior to calculating the change from baseline and determine if the “change score” attains normality. If this transformation is not successful, the median of the change will be calculated along with the 95% confidence interval for the median using Hodges-Lehmann estimators. Each confidence interval will be visually inspected to determine if zero is a possible value for the true change from baseline (μ). This corresponds to testing the following hypothesis:

H0: $\mu=0$ vs. H1: $\mu\neq 0$.

The last observation carried forward (LOCF) method will be used for participants who end the trial early.

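### The nonparametric fallback for the primary endpoint promises a 95% interval that five EoE-CTD participants cannot supply, and labels a pseudomedian interval as one for the median

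*SAP*

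**What the plan says.** The SAP, under Analysis of Primary Outcome, starts from the mean change in peak eosinophil count. If the changes are not normal, it moves to square-root counts. If those fail too, "the median of the change will be calculated along with the 95% confidence interval for the median using Hodges-Lehmann estimators". Protocol 12.4 has the same sentence.

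The interval is needed three times: "The average change from baseline within each group and combining both groups (i.e. EoE and EoE-CTD) will be calculated", and the plan attaches a two-sided interval at the 95% level to each. Each interval is then looked at to see whether it contains zero, which the plan equates with testing a true change of zero. On the error rate, the SAP Overview says "Unless stated otherwise, all statistical testing will be done at" 0.05.

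On group sizes, Protocol 12.5 says "Five patients with EoE-CTD and 10 patients with EoE will be recruited into the study". The Synopsis (Accrual Objective) says that of about 15 enrolled "at least one third will have evidence of EoE with CTD", so five is the planned minimum for that group.

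The SAP also adds a paired Wilcoxon test, for the whole cohort and by CTD stratum, at 0.05. The plan does not say whether the Hodges-Lehmann interval or the Wilcoxon p-value is exact or approximate, and it does not assume that the changes are symmetric.

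**The concern.** Two things in one sentence need separate treatment.

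- **Confidence level at n=5.** The one-sample Hodges-Lehmann interval inverts the signed-rank test. With very few participants that test has few attainable levels, and at n=5 none reaches 95%. An interval printed as 95% and checked for zero would carry more than the stated 5% error in the EoE-CTD group. It could also disagree with the Wilcoxon test that the SAP runs on the same five changes.
- **Target of the interval.** The method estimates the pseudomedian, which is the median of the average of two independent changes. It equals the median when changes are symmetric. The fallback is used only after normality has failed twice, so symmetry cannot be taken for granted. Protocol 12.5 intends the effect estimates to power later studies, so a reader needs to know which quantity was estimated.

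**Working it through.** **Inputs.** Group sizes 5, 10 and 15 (Protocol 12.5); two-sided 95% and 0.05 (SAP); SD 5 or 10 on the square-root scale (Protocol Table 7). I take the SAP's paired Wilcoxon test to be the signed-rank test.

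**The plan's own figures.** Table 7 gives the only planning figures for the primary interval, and they are for the mean. With half-width t(0.975, n-1) × SD / √n:

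| n | t | SD 5 | SD 10 | Table 7 |
|---|---|---|---|---|
| 15 | 2.145 | 2.77 | 5.54 | 2.8, 5.5 |
| 10 | 2.262 | 3.58 | 7.15 | 3.6, 7.2 |
| 5 | 2.776 | 6.21 | 12.42 | 6.2, 12.4 |

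All six agree. There is no figure for the fallback.

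**Attained confidence of the fallback.** With n changes there are 2^n equally likely sign patterns and n(n+1)/2 pairwise averages, counting each change with itself. The interval runs from the k-th smallest to the k-th largest average. Its exact confidence is 1 - 2 × P(signed-rank statistic ≤ k-1).

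- n=5: the widest choice is k=1 (minimum to maximum), giving 1 - 2 × 1/32 = 93.75%. No wider interval exists.
- n=10: k=9 of 55 averages, giving 1 - 2 × 25/1024 = 95.1%.
- n=15: k=26 of 120 averages, giving 1 - 2 × 785/32768 = 95.2%.
- Neighbouring sizes: n=4 gives at most 1 - 2/16 = 87.5%; n=6 gives 1 - 2/64 = 96.9%.

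The normal approximation does not help at n=5. The statistic has mean 5 × 6/4 = 7.5 and SD √(5 × 6 × 11/24) = 3.71, so the lower rank is 7.5 - 1.96 × 3.71 = 0.23, below the first average.

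**Conflict with the Wilcoxon test.** If all five changes are negative, the minimum-to-maximum interval lies below zero and the visual check rejects. The exact two-sided p is 2/32 = 0.0625, which does not reject at 0.05. A large-sample p would be 0.043 without continuity correction (7.5/3.71 = 2.02) or 0.059 with it (7/3.71 = 1.89), so the unstated choice of method also decides the result.

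**Would an interval for the sample median avoid the limit?** No. At n=5 the binomial order-statistic interval is also minimum to maximum, with 93.75%. At n=10 and n=15 it attains 97.9% and 96.5%.

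**Median against pseudomedian.** An invented n=5 example with changes -80, -60, -10, -5, -2 has sample median -10, Hodges-Lehmann estimate -32.5 and interval -80 to -2.

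For coverage, the documents give no responder rate, so a mixture was assumed: baseline lognormal with median 45, truncated at 15; responders keep 0-25% of baseline; the others vary around baseline with log SD 0.35. Coverage of the true median by the nominal 95% interval at n=10-15 was:

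- Raw counts: 94-96%, with median and pseudomedian 1.4 to 2.8 eos/HPF apart.
- Square-root scale, 20-60% responders: 89-96%. At 40% responders the median was -1.08 and the pseudomedian -1.79, with coverage 92% (n=10) and 89% (n=15).
- Keeping only samples that would reach the fallback (assumptions: Shapiro-Wilk at 5% on both scales, baseline log SD 0.6): about 97% in the 40%, n=15, square-root case. Across cases at n=10-15 the range was 92-98% on raw counts and 87-97% on the square-root scale. The 87% (60% responders, n=15) rests on about 126 samples.

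Other assumed skewed shapes gave 92-94% at n=10 and 89-94% at n=15, while coverage of the pseudomedian stayed near 95%.

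**The case against.** The strongest reply is that this is a conditional fallback in a pilot that was not sized for testing, that a paired Wilcoxon analysis is planned regardless, and that the combined n=15 interval attains 95%. All of that stands and keeps the point modest. It does not make the printed 95% correct for EoE-CTD.

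A reader might infer more than the documents support:

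- **That a sample median is certainly paired with an interval for something else.** The text never says sample median. The reference to Hodges-Lehmann estimators can cover the point estimate too; then estimate and interval match and only the label is wrong. Even on the other reading, the sample median fell outside the interval in none of 20,000 simulated runs per case.
- **That the n=5 limit comes from choosing Hodges-Lehmann.** It comes from having 32 sign patterns, and the order-statistic interval has the same limit. Changing the estimator would not remove it.
- **That coverage drops to 89%.** That figure needs an assumed mixture and the square-root scale, which the plan has abandoned by then, and it does not condition on reaching the fallback.
- **That the zero check is invalid everywhere.** If baseline and final counts are exchangeable, changes are symmetric about zero, median and pseudomedian are both zero, and the check is valid at the attained level. At n=10 and n=15 that level is about 95%.

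**Conclusion.** The point holds as two separate, small defects.

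The first is arithmetic. At the planned five EoE-CTD participants, the exact interval has at most 93.75% confidence, so neither a 95% interval nor a 5%-level zero check is available there, and five changes of the same sign give opposite answers from the interval and the exact Wilcoxon test. It applies if the fallback is reached and exactly five are analysed. Six would attain 96.9%. Four, which could arise because the SAP's analysis population drops participants who change their baseline EoE treatment, would allow only 87.5%.

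The second is a labelling error: the interval is for the pseudomedian, and the plan makes no symmetry assumption that would turn it into one for the median. Its effect on coverage rests on assumed distributions. It is about nominal on raw counts and a few points short in some square-root scenarios. Neither defect undermines the EoE or combined intervals, provided they are read as intervals for the pseudomedian.

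**What to change.** Replace the fallback sentence in the SAP, and align Protocol 12.4, so that it:

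1. names the estimate as the Hodges-Lehmann pseudomedian of the changes, with its exact signed-rank interval, which agrees with the paired Wilcoxon test already in the SAP;
2. says that the Wilcoxon p-value is exact;
3. prints the attained confidence for each group: 93.75% at n=5, 95.1% at n=10, 95.2% at n=15, recomputed for the numbers actually analysed;
4. says that the n=5 interval is descriptive and is not read as a 5%-level test.

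If the team prefers the sample median, the order-statistic interval is the matching choice, but items 3 and 4 are still needed at n=5. No data collection or sample size changes. The cost is a few words in the SAP and one printed confidence level that looks slightly less favourable.

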### 2. Inclusion Criteria

Participants must meet all of the following inclusion criteria to be eligible for participation in this study.

1. Written informed consent has been provided by the participant /parent or legal guardian.
2. Participants (of any gender and any race) aged  $\geq 5$  years to  $\leq 25$  years at time of screening.
3. The participant has confirmed, active EoE (within 12 weeks prior to enrollment) as defined by esophageal mucosal eosinophils  $\geq 15$  per HPF (400 x magnification) confirmed by the research pathologist AND fits into one of the following categories:
  - a. Participant has not been diagnosed with and does not display phenotypes suggestive of a CTD, or
  - b. Participant has been diagnosed with a CTD (e.g., MFS, LDS, EDS, or hypermobility syndromes).
4. The participant has been on a high dose of PPI (at least one dose, once daily) for at least 8 weeks prior to a diagnostic endoscopy of EoE without histologic resolution (i.e.,  $\geq 15$  eosinophils/HPF). Due to the variety of doses and various PPIs available, the dose will be confirmed adequate at the discretion of the site PI.  
Note: Participants may continue with their acid reflux therapy as long as the dose remains the same throughout the study.
5. Participant must maintain the same diet, swallowed steroid, and PPI therapies throughout the duration of the study. Participants with active EoE on these therapies may be included in the study, as long as they agree to maintain the same diet, swallowed steroid, and PPI therapies.
6. At the time of study entry, a female participant is eligible if she meets one of the following criteria:

- a. Is of non-childbearing potential (pre-menarchal or surgically sterile with documentation);
- b. Is of childbearing potential with a negative urine pregnancy ( $\beta$ -hCG) prior to enrollment into the study (i.e., at screening) and at each study visit. Subsequently, these participants must agree to use adequate birth control measures (e.g., condom, oral / injectable / subcutaneous contraceptives, intrauterine device, or sexual abstinence) during the study and for at least one month after the last dose of study drug, which will be documented in the source documents.

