8.12 Table 4: Study Design and Schedule of Assessments

PHASE	PRE-TREATMENT PHASE	Titration Phase a,c		TREATMENT PHASE			EOT or Early Withdrawal	FOLLOW-UP PHASE	
	1	2	2a	3	Maintenance Phase				6
Visit Number	1	2	2a	3	3a	4	5	6	7
Visit Description	Screening	Enrollment Baseline	Week 1 Visit Check BP/AEs	Visit 3 Up-titration	Phone call	Maintenance Month 2	Maintenance Month 3	EOT Visit	Safety Phone call
Week	-12 to 0	0	1	4	5	8	12	16	20
Perform informed consent/assent	X								
Assess eligibility (inclusion/exclusion criteria)	X	X							
Obtain medical, surgical, dietary history, & demographics	X								
Vitals (height, weight, blood pressure, heart rate, respiratory rate, temperature)	X	X		X		X	X	X	
Physical exam	X			X				X	
SOCEGD with biopsies/EREPS	X a							X	
EndoFLIP e	X							X	
PedsQL™ EoE Module h		X		X		X	X	X	X
FEESV 2.0 i		X		X		X	X	X	X
EESal		X		X		X	X	X	X
EoE-QoL-Adult		X		X		X	X	X	X
Participant Intake Form		X							
Clinical laboratory samples	X			X		X	X	X	
Research laboratory samples	X d							X d	
Urine pregnancy test l	X			X		X	X	X	X
Assess AEs		X	X	X	X	X	X	X	X
Assess concomitant medications and/or therapies		X	X	X	X	X	X	X	X
Dispense study drug, drug diary, and instructions		X		X		X	X		
Determine compliance with study drug				X		X	X	X	
Collect unused study drug				X		X	X	X	

a First EGD used to determine eligibility may be conducted within 12 weeks prior to enrollment visit.

b At each monthly or titration visit, the participant must have been on previously dispensed dose of study drug for at least 21 days but no more than 28 days.

c Clinical labs: CBC with differentials, chemistry panel, and IgE (first and last visit only).

d Research labs: mRNA in blood and tissue, TGF- $\beta$  in blood and tissue.

e In addition to assessing diet and concomitant medication compliance at each scheduled visit, research personnel will also conduct one telephone call per month to assess compliance during the maintenance phase. During the titration phase, diet and concomitant medication compliance will be conducted during scheduled phone calls (Visits 2a and 3a).

f Participants who withdraw from the study before completing the maintenance phase should complete the EOT/early withdrawal visit, including SOCEGD and biopsy, within two weeks of the last dose of study drug.

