Additionally, to evaluate the effect of losartan on the reduction of esophageal eosinophils in participants with EoE (with or without a CTD), we will use paired non-parametric Wilcoxon Rank sum test. The Wilcoxon rank sum paired test will be used given the small sample size and the broad range of eosinophils which could be present in our participants. Analyses will be performed using the whole cohort and stratified by CTD. Statistical significance will be set at $\alpha = 0.05$. This corresponds to testing the following hypothesis:

H0: baseline and study completion are equal vs. H1: baseline and study completion are not equal.

Analyses of Secondary Endpoint(s)/Outcome(s)

To assess changes over time for continuous secondary and safety outcomes, a mixed effects model for repeated measures analysis will be used. The dependent variable will be the change from baseline. The “participant nested within group” term will be considered a random effect. Time (i.e. measurement time) will be included as a continuous effect. Terms in the model will be time, group (i.e., EoE and EoE-CTD), and time-by-group interaction. The baseline value will be used as a covariate in the model. If necessary, to meet the assumptions of the analysis, an appropriate transformation will be used (e.g., square root, log, rank). The hypotheses that will be tested are whether there is a significant trend over time and whether this trend is consistent between the CTD and non-CTD groups (i.e. testing the interaction term). If the trend is not consistent between groups based on the statistical test at $\alpha=0.10$, we will estimate the trend within each of the two groups by including terms in the statistical model that estimates the trend within each group and the hypothesis to be tested within each group is whether this trend is significantly different than zero. We will systematically assess the residuals to determine whether a linear or quadratic model best fits the data. In statistical terms, the hypotheses are provided below.

For testing consistency of the time trend (β) between the CTD and non-CTD group, the hypotheses are:

H0: $\beta_{\text{EoE-CTD}} = \beta_{\text{EoE (non-CTD)}}$ vs. H1: $\beta_{\text{EoE-CTD}} \neq \beta_{\text{EoE (non-CTD)}}$.

For testing linear trend combining across groups (if there is consistency of the time trend):

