H0: $\beta=0$ vs. H1: $\beta\neq 0$ where β is the slope of the line across groups. Similar hypotheses will be tested if analysis of the residuals indicates that higher order terms need to be included in the model (e.g. quadratic). If there is strong evidence that the time trend is not consistent between the two groups, we will test the above hypothesis within each of the two groups. In addition, the two-sided, 95% confidence interval for the slopes will be calculated to provide estimates of the slope for future studies.

The percentage of participants for whom peak eosinophil counts are < 15 eosinophil/HPF at Week 16 will be estimated within each CTD group along with a 95% confidence interval.

Safety endpoints that are categorical will be summarized within each group. Further, any SAEs or Grade 3 or above will be reported descriptively.

Software Used (with References) and Specialized Macros (with References)

SAS version 9.4, JMP 14.

This SAP has been reviewed and approved by:

Investigator

Date

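### The biopsy that qualifies a participant is also the only baseline, so some fall in eosinophils is expected without a losartan effect, and a change excluding zero cannot by itself be credited to the drug

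*SAP*

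**What the plan says.** **Entry.** Protocol 4.2, criterion 3, requires "confirmed, active EoE (within 12 weeks prior to enrollment) as defined by esophageal mucosal eosinophils" of at least 15 per HPF.

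**Baseline.** Protocol Table 4 (8.12) schedules endoscopy only at screening and at end of treatment. Its footnote a reads: "First EGD used to determine eligibility may be conducted within 12 weeks prior to enrollment visit". Section 8.1 allows an outside endoscopy that settles eligibility to serve as the baseline as well. Section 5.4.3 rules out extra endoscopies for the study, and section 12.3 assigns every participant to losartan. So there is one pre-treatment reading and no control.

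**Decision rule.** The SAP, Analysis of Primary Outcome (and Protocol 12.4), sets H0: μ = 0: "Each confidence interval will be visually inspected to determine if zero is a possible value for the true change from baseline". The SAP then adds a paired Wilcoxon test, "to evaluate the effect of losartan on the reduction of esophageal eosinophils in participants", with null "H0: baseline and study completion are equal".

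**Responders.** "The percentage of participants for whom peak eosinophil counts are < 15 eosinophil/HPF at Week 16 will be estimated" with a confidence interval. No reference rate is given.

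**Use of the result.** Protocol 12.5: "The estimates of treatment effect from this study will be used to power future studies".

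Neither document mentions regression to the mean or a change expected without the drug.

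**The concern.** Peak eosinophil count varies from one endoscopy to the next. A rule that admits people because one reading reached 15, and then uses that reading as baseline, selects partly on upward fluctuation. The next reading will be lower on average even if losartan does nothing. In this sample, then, no losartan effect is not the same hypothesis as μ = 0.

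The same selection bears on the proportion below 15. Everyone starts at 15 or more by rule, so any crossing counts as a response, including crossing by chance.

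Two things are at stake. An interval excluding zero, or p < 0.05, could be reported as a losartan effect. And an estimate biased towards benefit would go into planning the next trial, making that trial too small.

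**Working it through.** **1. The plan's own figure.** Table 7, n = 15, SD 5 on the square-root scale: half-width = t(0.975, 14) × 5/√15 = 2.145 × 1.291 = 2.77, printed as ±2.8. All six entries reproduce. The documents state no error rate and no expected null change for this test.

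**2. Direction.** Let Y1 and Y2 be the two readings, interchangeable if disease is stable and the drug inert, and let c be the cut. Participants with both readings at or above c contribute zero to the mean change by symmetry. What remains is

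E[Y2 − Y1 | Y1 ≥ c] = −P(Y2 < c | Y1 ≥ c) × E[Y1 − Y2 | Y1 ≥ c, Y2 < c].

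This is negative whenever anyone can cross the cut by chance, on the raw or the square-root scale. The null fall and the null rate below 15 come from the same people.

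**3. What the documents fix about size.** Cut 15; n = 15; two-sided 0.05; planning SD of change about 5 (square-root scale). The accrual estimate is "30 patients will need to be screened for a total of approximately 15 participants enrolled", or 15/30 = 50% overall, with no reasons for failure. So the share passing on histology lies between 50% and 100% of those counted as screened. Section 8.1 also describes pre-screening from records, which could make the real selection stronger. Within-person variability is not given.

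**4. Count model (assumed).** Lognormal person and visit effects with Poisson counts; person medians 15, 30 and 45 eosinophils/HPF; between-person log SD 0.7–0.8; within-person log SD 0.5–1.0; no drug effect; n = 15. The paired Wilcoxon is taken as the signed-rank test.

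| Share passing the cut | Square-root t | Wilcoxon | Raw-count t | Below 15 at second reading |
|---|---|---|---|---|
| about 50% | 19–28% | 14–24% | 11–13% | up to about 38% |
| 71–78% | 8–11% | 8–11% | 5% | 13–22% |
| 81–89% | 4–7% | 4–7% | near nominal | 7–15% |

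Other choices of the SDs move the ends by a few points. At half passing they give 16–29% (square-root t), 13–26% (Wilcoxon) and 26–39% below 15. At 71–79% passing they give 7–12% and 6–11%.

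**5. Second model, wider range (assumed).** Normal on the square-root scale, clipped at zero: person mean 4–9, between-person SD 1.5–2.5, baseline kept if at least √15 = 3.873, square-root t interval, n = 15.

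| Within-person SD | Mean null change | Rejection | Below 15 |
|---|---|---|---|
| 1 | 0.0 to −0.4 | 5–20% | 0.2–24% |
| 2 | −0.1 to −1.2 | 5–41% | 2–37% |
| 3.54 | −0.6 to −2.3 | 7–55% | 9–44% |

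The value 3.54 = 5/√2 treats the whole planning SD as within-person noise, so it is an upper value. Where inflation is clear, almost all of it points to benefit (25.6 of 25.7 percentage points in one scenario). The subgroups are less affected: about 5–38% at n = 10 and 5–18% at n = 5.

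**6. Cause.** In five of these scenarios the baseline was redrawn from a reading separate from the qualifying one. Mean null change became 0.0 and rejection 4.9–5.3%. The share below 15 did not fall (1.4–43.9%), so that rate needs a reference in any case.

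**The case against.** **It is a declared descriptive pilot.** Protocol 2.1 says so, 12.5 says the size was not chosen for testing, and an uncontrolled change can never isolate a drug. This is fair, and correcting for regression alone would not isolate losartan either. But the SAP sets hypotheses and α = 0.05 and ties the paired test to the effect of losartan, and 12.5 sends the estimate into future planning. The label does not remove the bias.

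**The size is unknown.** This stands. A reader might infer that the test will reject under no effect; in nearly every scenario above non-rejection is the likelier outcome. A reader might take the 15 failures in 30 as histologic, but there are 18 exclusion criteria and no stated reason for failure. A reader might conclude that error is at least doubled once 70% or fewer pass; the models give 6–12% at 71–79%.

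**The simplest formula exaggerates.** A normal model with SD of change 5, half passing and correlation 0.5–0.8 gives a null change of −2.0 to −1.3 and rejection of 34–16%. It also puts 22–31% of square-root counts below zero, so it is not used here.

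**Some features dilute the bias.** LOCF with no later biopsy sets the change to zero. Criterion 4 may mean that an earlier biopsy was also at least 15, which in the second model lowers the range to 5–47%. The raw-count interval, the plan's first choice, is less affected. All of this stands, but the Wilcoxon test is planned whatever the scale.

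**The plan never tests the below-15 rate against zero.** Correct: it is only estimated. The gap is the missing reference.

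**Conclusion.** The point holds in restricted form. The qualifying biopsy is the only baseline and there is no control, so with any visit-to-visit variability the expected change is below zero when losartan does nothing. An interval excluding zero, or a significant paired test, shows change from the qualifying biopsy and cannot by itself be read as a losartan effect. The below-15 rate has a no-effect value above zero and no reference in the plan.

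The direction assumes only stable disease and some visit-to-visit variability. The size depends on inputs the documents do not give. Under the count models, false rejection (Wilcoxon or square-root t) is about 14–28% if about half pass on histology, about 8–11% if 70–80% pass, and near nominal above that, with about 7–38% falling below 15.

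The documents do not support going further and replacing the primary null with a registry value. Section 1.1 describes a registry of 1,008 EoE patients, but nothing shows that it holds paired endoscopies on unchanged therapy. The planned estimate can stay; its reading needs to change.

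**What to change.** Keep the planned estimate and interval. In the SAP, Analysis of Primary Outcome, and Protocol 12.4:

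- **(a)** Add a pre-specified sensitivity analysis that sets the observed change and the below-15 rate beside the values expected with no drug effect. Derive these from a truncation (regression-to-the-mean) model on a non-negative count scale, over a stated range of within-person correlation. Use registry pairs on unchanged therapy as well only if such pairs prove to exist.
- **(b)** State that an interval excluding zero shows change from the qualifying biopsy, not an effect of losartan.

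In Protocol 12.5:

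- **(c)** Carry the corrected range, not only the raw change, into the powering of future studies.

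The cost is text and a small analysis, with no added endoscopy and no added participants. The downside is that the reported effect becomes smaller and less certain, and the correction rests on an assumed correlation.
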